Following SBRT, MK-3475 will be re-started and administered in 3-week cycles as quickly as feasible. Dose modifications or delays may be made per section 5.2.2, based on prior toxicity from the first course of drug treatment. Treatment will continue until progression of disease, which **will be defined for this purpose as progression in comparison to the tumor imaging obtained immediately before or after SBRT (whichever is more recent)**. At the discretion of the principal investigator, patients may continue to receive treatment if they are receiving clinical benefit. For the purpose of measuring response, the irradiated lesion will no longer qualify as measurable disease.

Progression of Disease (irPD) for this study will be defined using the Immune-Related Response Criteria (irRC), with the following qualification:

Radiographic progression of disease by RECIST criteria (but not by irRC) where, in the opinion of the investigator, the patient would no longer benefit from continuing drug therapy, will be considered progression of disease.

During the **pre-SBRT** MK-3475, radiation to isolated sites of metastatic disease is not permitted.

During the **post-SBRT** MK-3475, local surgery and/or radiation therapy to isolated sites of metastatic disease is permitted and the patient can continue the MK-3475 provided there is evidence of continuing benefit from systemic treatment (i.e., stable disease or response in at least one other measurable lesion, or clinical improvement).

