**At the maximum dose level, STOP, this is the MTD

Definition of Dose Limiting Toxicity

For the purpose of determining the MTD of SBRT, a DLT will be considered to be any of the following adverse events which are probably or definitely attributable to study treatment, and which occur between the first fraction of SBRT and within 60 days of the last fraction of SBRT.

1. Any non-hematologic, non-laboratory toxicity which is grade 3 or greater and does not resolve to grade 2 or lower with supportive care within 14 days.
2. Any non-hematologic, non-laboratory toxicity which is grade 4 or greater
3. For patients in Arm A (lung targets), the development of grade 3 or greater pneumonitis that is probably or definitely attributable to either SBRT or MK-3475 within the follow-up period will be considered a DLT, regardless of whether it resolves.

54 Concomitant Medications/Vaccinations (allowed & prohibited)

Acceptable Concomitant Medications

All treatments that the investigator considers necessary for a subject's welfare may be administered at the discretion of the investigator in keeping with the community standards of medical care. All concomitant medication will be recorded on the case report form (CRF) including all prescription, over-the-counter (OTC), herbal supplements, and IV medications and fluids. If changes occur during the trial period, documentation of drug dosage, frequency, route, and date may also be included on the CRF.

All concomitant medications received within 28 days before the first dose of trial treatment and 30 days after the last dose of trial treatment should be recorded. Concomitant medications administered after 30 days after the last dose of trial treatment should be recorded for SAEs as defined in Section 7.2.

Prohibited Concomitant Medications

Subjects are prohibited from receiving the following therapies during the Screening and Treatment Phase (including retreatment for post-complete response relapse) of this trial:

- Anti-cancer systemic chemotherapy or biological therapy
- Immunotherapy not specified in this protocol
- Chemotherapy not specified in this protocol
- Investigational agents other than MK-3475
- Radiation therapy except for that specified by protocol

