12.0 MEASUREMENT OF RESPONSE

Response will be evaluated by imaging studies as described in the study calendar. If symptoms develop or clinical deterioration occurs, patients may be imaged prior to the pre-specified time points for imaging.

Response of all systemic metastases will be evaluated in this study using two methods: the new international criteria proposed by the Response Evaluation Criteria in Solid Tumors (RECIST) Committee v1.1, and the Immune-Related Response Criteria (irRC). The irRC will be used to make protocol-related decisions regarding treatment response. Response by RECIST will be recorded for later analysis. RECIST version 1.1 stipulates that the number of lesions required to assess tumor burden for response determination has been reduced to a maximum of five total lesions (two lesions maximum per organ).

Briefly, measurable lesions must have a minimum size of 10 mm by CT scan (CT scan slice thickness no greater than 5 mm) in at least one dimension. Lesions with a longest diameter of <10 mm are considered non-measurable lesions and will be tracked as non-target disease. Tumor lesions in a previously irradiated area, or in an area subject to other loco-regional therapy, are not considered measurable unless there has been demonstrated progression in the lesion. Following SBRT, response will be measured in comparison to the most immediate pre-

SBRT imaging study, or imaging immediately following SBRT, whichever is most recent. For this purpose, the metastatic target chosen for SBRT will not qualify as a measurable lesion. For complete definitions of measurable and non-measurable disease, please refer to the RECIST v1.1 criteria.

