12.1 Evaluation of Best Overall Response

The Best Overall Response is the best response recorded from the start of the treatment until disease progression/recurrence (taking as reference for progressive disease the smallest measurements recorded since the treatment started). For purpose of the primary endpoint of the study, the overall response will be measured during the post-SBRT MK-3475, in comparison to the most immediate pre-SBRT imaging.

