12.2 Progression-Free and Overall Survival

For the purpose of the secondary endpoints of this study, PFS is defined as the time from initiation of study drug post-SBRT, until the first documented, confirmed progression of disease as described in Section 5. PFS will also be measured and report from the initiation of study drug, pre-SBRT. OS will be measure from the initiation of study therapy.

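### Response and PFS continue to be scored after surgery or radiation to lesions other than the SBRT target, and the plan has no rule for attributing what follows

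*Combined protocol and SAP*

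**What the plan says.** Section 5.2.1 treats the two courses of MK-3475 differently. Before SBRT, radiation to isolated metastatic sites is not allowed. After SBRT, "local surgery and/or radiation therapy to isolated sites of metastatic disease is permitted and the patient can continue the MK-3475". A condition is attached to this permission: the drug may go on "provided there is evidence of continuing benefit from systemic treatment". Stable disease or response in one other measurable lesion meets that condition, and so does clinical improvement.

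The endpoint sections cover the same period:

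- Section 12.1, primary endpoint: "the overall response will be measured during the post-SBRT MK-3475, in comparison to the most immediate pre-SBRT imaging". Best response is the best recorded up to progression.
- Section 12.2: PFS runs from the first post-SBRT dose "until the first documented, confirmed progression of disease as described in Section 5".
- Section 12.0: lesions at sites irradiated earlier, "or in an area subject to other loco-regional therapy, are not considered measurable unless there has been demonstrated progression in the lesion". The only exclusion written specifically for the post-SBRT assessment is that "the metastatic target chosen for SBRT will not qualify as a measurable lesion".
- Section 9.0: the strategy is judged worth pursuing if 4 of 20 NSCLC patients respond, against a presumed rate without SBRT of less than 5%. The analyses are a proportion with a confidence interval, an exact binomial test and a Kaplan-Meier curve for PFS.

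None of these sections says how local therapy to a lesion other than the SBRT target enters response or PFS.

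**The concern.** The phase 2a question is whether SBRT to one lesion, followed by MK-3475, produces a systemic response. The plan protects that question at two points: it bars radiation to other sites before SBRT, and it takes the SBRT target out of the measurable disease. It gives no matching protection against further surgery or radiation after SBRT, although that is when the endpoint is measured.

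Few lesions may carry the assessment. Entry requires only two measurable sites, so once the SBRT target is excluded a single measurable lesion may remain. The decision turns on four responders, so one misattributed response can change it.

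**Working it through.** The plan gives no figure on this point: no frequency of local therapy and no error rate for the 4-of-20 rule. The check is therefore a reading of the rules, followed by an illustration under stated assumptions.

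**1. What happens to the treated lesion.** Section 12.0 makes it non-measurable, with an exception for demonstrated progression in the lesion. It is not clear whether growth before the local treatment meets that exception. Nor does the plan say whether a dropped lesion leaves the baseline sum as well as the follow-up sum.

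Assumed sizes: lesion A is 30 at baseline. Lesion B is 20 and grows to 26, and is then treated locally. Change = follow-up sum / baseline sum − 1.

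| Handling of B | A shrinks to 18 | A stays at 30 |
|---|---|---|
| Counted at its grown size | (18+26)/50 − 1 = −12% | (30+26)/50 − 1 = +12% |
| Dropped from both time points | 18/30 − 1 = −40% | 30/30 − 1 = 0% |
| Dropped from follow-up only, or kept measurable and resected to 0 | 18/50 − 1 = −64% | 30/50 − 1 = −40% |

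Consistent dropping removes growth from the sum but needs shrinkage in A before there is any decrease. Keeping B measurable lets its removal appear as a decrease even when A is unchanged.

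**2. Attribution when A does shrink.** The trial's own hypothesis (Sections 3.0 and 4.5) is that radiation to one site may provoke regression elsewhere. A second course of radiation to B is then a competing explanation for shrinkage in A.

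**3. PFS.** If irPD has been documented and confirmed, the event precedes the local therapy and PFS is not changed. Section 5.2.1 also counts RECIST-only progression when the investigator sees no further benefit from the drug. The remaining route to a delayed event is local treatment of a lesion below the irPD threshold or before confirmation.

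**4. Effect on the decision rule.** Inputs: n = 20 and threshold 4 (Section 9.0); true rate 0.05, the upper end of the stated range. The number of artefactual responders is an assumption.

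- None: P(X ≥ 4 | 20, 0.05) = 1 − Σ(k=0 to 3) C(20,k) 0.05^k 0.95^(20−k) = 1 − 0.98410 = 0.016.
- One: the other 19 must supply 3. P(X ≥ 3 | 19, 0.05) = 1 − 0.93345 = 0.067.
- Two: the other 18 must supply 2. P(X ≥ 2 | 18, 0.05) = 1 − 0.77352 = 0.226.

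As an alternative, give each true non-responder a chance f of an artefactual response, so that the apparent rate is 0.05 + 0.95f:

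| f (assumed) | Apparent rate | P(X ≥ 4 of 20) |
|---|---|---|
| 0.02 | 0.069 | 0.045 |
| 0.05 | 0.0975 | 0.124 |
| 0.10 | 0.145 | 0.328 |

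**The case against.** The strongest reply is that the plan already limits the damage. Best response closes at progression, and confirmed irPD is a PFS event whatever is done afterwards. If a treated lesion is dropped from both time points, a response still needs shrinkage in other unirradiated lesions, which is close to what the trial wants to observe. Non-measurable disease is not necessarily ignored either: Section 12.0 tracks lesions under 10 mm as non-target disease and refers to RECIST 1.1 for the full definitions. Most of this stands, and it limits the point. It does not answer the attribution problem, or the case where the lesion stays measurable under the exception.

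A reader might infer more than the documents support:

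- That Section 12.0 always removes a growing lesion and so creates a response. The exception for demonstrated progression leaves this open, and consistent removal gives 0% change when the other lesion is stable. Section 5.2.1 also speaks of isolated sites and does not say that they are growing.
- That Section 5.4 contradicts the permission. Its prohibited list reads "Radiation therapy except for that specified by protocol". Section 5.2.1 specifies this radiation, so the exception covers it, and surgery is not on the list.
- That the needed dates are already collected. Section 5.4 requires concomitant medication on the case report form. No section shows that local surgery or radiation is recorded there.

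The continuing-benefit condition governs whether the drug continues. It does not say how endpoints are scored.

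**Conclusion.** The point holds as a gap in the endpoint rules. Followed as written, the plan can credit to SBRT plus MK-3475 responses, and in a narrower set of cases progression-free time, that other local treatment helped to produce. For response, this is so under either reading of the Section 12.0 exception. A general claim that PFS is inflated is not supported.

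The size is unknown because the documents do not say how often such treatment is expected. The probabilities of 0.067 and 0.226, against 0.016, assume exactly one or two artefactual responders among 20. They also assume a true rate of 5%; the plan presumes less than 5%, and all three would be lower at a lower rate. They show how sensitive a four-responder threshold is and do not predict a false-positive rate. The change is worth making because it costs little and bears on the primary decision.

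**What to change.** - **Sections 9.0 and 12.1:** score the primary response only on scans taken before the first surgery or radiation to any lesion other than the SBRT target. Report response under the current definition as a sensitivity analysis.
- **Section 12.2:** keep the current PFS definition. Add a sensitivity analysis that counts such local therapy, when given for lesion growth, as an event on its date. This belongs in a sensitivity analysis because it depends on judging why the therapy was given and can count patients without irPD as progressed.
- **Data collection:** record the date and reason of any such local therapy.

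The treatment permission in Section 5.2.1 and the list in Section 5.4 need no change for this purpose.

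The cost is a few sentences of analysis text and possibly a small addition to the case report form. The downside is that a true systemic response first seen after local therapy is left out of the primary analysis. It would still appear in the sensitivity analysis.

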5.2.2 MK-3475 Dose and Dose Modification

Drug Dose & Storage

Clinical Supplies will be provided by Merck & Co., Inc., as summarized in table 3 below.

Table 3. Product Description

Product Name & Potency	Dosage Form
MK-3475 100 mg/ 4 mL	Solution for Injection

MK-3475 will be administered at 200 mg, by IV infusion, every 3 weeks (+/- 7 days) on day 1 of each cycle.

Dose Modification (Escalation/Titration/Other)

MK-3475 will be withheld for drug-related Grade 4 hematologic or laboratory toxicities, non-hematological toxicity \geq Grade 3, or severe or life-threatening AEs as per Table 4 below. If MK-3475 is held at any point during a subject's participation in the trial for any reason, the subject will be followed as per standard of care until treatment with MK-3475 is resumed. When treatment with MK-3475 is resumed, the subject will continue with Day 1 procedures for the next planned cycle.

Table 4: Dose modification guidelines for drug-related adverse events.

Toxicity	Hold Treatment For Grade	Timing for Restarting Treatment	Treatment Discontinuation
Diarrhea/Colitis	2-3	Toxicity resolves to Grade 0-1	Toxicity does not resolve within 12 weeks of last dose or inability to reduce corticosteroid to 10 mg or less of prednisone or equivalent per day within 12 weeks
	4	Permanently discontinue	Permanently discontinue
AST, ALT, or Increased Bilirubin	2	Toxicity resolves to Grade 0-1	Toxicity does not resolve within 12 weeks of last dose
	3-4	Permanently discontinue (see exception below) ^a	Permanently discontinue
Type 1 diabetes mellitus (if new onset) or Hyperglycemia	T1DM or 3-4	Hold pembrolizumab for new onset Type 1 diabetes mellitus or Grade 3-4 hyperglycemia associated with evidence of beta cell failure	Resume pembrolizumab when patients are clinically and metabolically stable
Hypophysitis	2-4	Toxicity resolves to Grade 0-1. Therapy with pembrolizumab can be continued while endocrine replacement therapy is instituted	Toxicity does not resolve within 12 weeks of last dose or inability to reduce corticosteroid to 10 mg or less of prednisone or equivalent per day within 12 weeks
Hyperthyroidism	3	Toxicity resolves to Grade 0-1	Toxicity does not resolve within 12 weeks of last dose or inability to reduce corticosteroid to 10 mg or less of prednisone or equivalent per day within 12 weeks
	4	Permanently discontinue	Permanently discontinue

Toxicity	Hold Treatment For Grade	Timing for Restarting Treatment	Treatment Discontinuation
Hypothyroidism		Therapy with pembrolizumab can be continued while thyroid replacement therapy is instituted	Therapy with pembrolizumab can be continued while thyroid replacement therapy is instituted
Infusion Reaction	2 ^b	Toxicity resolves to Grade 0-1	Permanently discontinue if toxicity develops despite adequate premedication
	3-4	Permanently discontinue	Permanently discontinue
Pneumonitis	2	Toxicity resolves to Grade 0-1	Toxicity does not resolve within 12 weeks of last dose or inability to reduce corticosteroid to 10 mg or less of prednisone or equivalent per day within 12 weeks
	3-4	Permanently discontinue	Permanently discontinue
Renal Failure or Nephritis	2	Toxicity resolves to Grade 0-1	Toxicity does not resolve within 12 weeks of last dose or inability to reduce corticosteroid to 10 mg or less of prednisone or equivalent per day within 12 weeks
	3-4	Permanently discontinue	Permanently discontinue
All Other Drug-Related Toxicity ^c	3 or Severe	Toxicity resolves to Grade 0-1	Toxicity does not resolve within 12 weeks of last dose or inability to reduce corticosteroid to 10 mg or less of prednisone or equivalent per day within 12 weeks
	4	Permanently discontinue	Permanently discontinue

Note: Permanently discontinue for any severe or Grade 3 drug-related AE that recurs or any life-threatening event.

^a For patients with liver metastasis who begin treatment with Grade 2 AST or ALT, if AST or ALT increases by greater than or equal to 50% relative to baseline and lasts for at least 1 week then patients should be discontinued.

^b If symptoms resolve within one hour of stopping drug infusion, the infusion may be restarted at 50% of the original infusion rate (e.g., from 100 mL/hr to 50 mL/hr). Otherwise dosing will be held until symptoms resolve and the subject should be premedicated for the next scheduled dose; Refer to **Error! Reference source not found.** – Infusion Treatment Guidelines for further management details.

^c Patients with intolerable or persistent Grade 2 drug-related AE may hold study medication at physician discretion. Permanently discontinue study drug for persistent Grade 2 adverse reactions for which treatment with study drug has been held, that do not recover to Grade 0-1 within 12 weeks of the last dose.

In case toxicity does not resolve to Grade 0-1 within 12 weeks of AE start date, trial treatment should be discontinued after consultation with the sponsor. With sponsor and principal investigator agreement, subjects with a laboratory adverse events still at Grade 2 after 12 weeks may continue treatment in the trial only if asymptomatic and controlled. For information on the management of adverse events, see Section 5.5.

Subjects who experience a recurrence of the same severe or life-threatening event at the same grade or greater with re-challenge of MK-3475 should be discontinued from trial treatment.

Timing of Dose Administration

Trial treatment should be administered on Day 1 of each cycle after all procedures/assessments have been completed as detailed on the Trial Flow Chart (Section 6.0). Trial treatment may be administered up to 7 days before or after the scheduled Day 1 of each cycle due to administrative reasons.

MK-3475 will be administered as a 30 minute IV infusion. Sites should make every effort to target infusion timing to be as close to 30 minutes as possible. However, given the variability of infusion pumps from site to site, a window of -5 minutes and +10 minutes is permitted (i.e., infusion time is 30 minutes: -5 min/ +10 min).

5.2.3 Stereotactic Body Radiation Therapy (SBRT)

Target Selection

Target selection for SBRT will occur after the patient develops progression of disease on the pre-SBRT treatment with MK-3475. For the Phase Ib portion, patients will be allocated to Arm A (Lung target) if the SBRT target overlaps the lung parenchyma, otherwise patients will be allocated to Arm B (Non-Lung target). Targets suitable for SBRT for all phases of the study must meet all of the following requirements. Melanoma and NSCLC patients with prior treatment on anti-PD1 therapy will only be enrolled if there is a suitable target. In NSCLC patients initiating MK-3475 as first protocol treatment, if there are no suitable targets for SBRT after the pre-SBRT MK-3475, the patient may be observed and interval re-imaging may be obtained at the discretion of the investigators. Patients who cannot be treated with SBRT within 12 weeks of the most recent infusion of MK-3475 will be taken off treatment and moved to survival follow up. Exceptions to the 12 week window may be allowed for individual patients at the discretion of the Principal Investigator. MK-3475 may be administered after progression has been determined while SBRT is planned. Additionally, target lesions:

1. Must not be located in the liver, small or large bowel
2. Treatment must be accomplished without exceeding any normal tissue dose limit, as defined in the report of the American Association of Physicists in Medicine, Task Group 101 report[55].

SBRT Planning

Patients will undergo CT simulation and treatment planning per standard practice. Patient immobilization should be sufficient to ensure minimal intra- and inter-fraction set-up error, and is otherwise left to the discretion of the treating radiation oncologist. For lung targets, a technique for motion management is required, which may include tumor tracking, respiratory gating, or 4D-CT simulation. The treating physician will define a planning target volume (PTV) to which the dose will be described, and which will be used to define local control or local failure. At least 90% of the PTV should receive 90% or more the prescription dose. All organs at risk within 5 cm of the PTV will be contoured, and dose-volume histograms produced. For all organs at risk contoured, dose limits will be followed without exception[55].

SBRT Treatment Administration

The first fraction of SBRT should be delivered as soon as feasible after progression of disease. For the following events, SBRT should be delayed until they resolve (for toxicities, to grade 0 or 1), up to 12 weeks after the last infusion of MK-3475. If the listed events do not resolve within 12 weeks of the last infusion of MK-3475, the patient will be removed from the study and replaced.

1. Grade 2 or greater pneumonitis
2. Corticosteroid use within 2 weeks of SBRT, except in individual cases allowed by the Principal Investigator
3. Grade 3 or greater non-hematologic toxicity related to study therapy

Patients who develop grade 3 or greater pneumonitis during the pre-SBRT MK-3475 will be taken off of the study, and will not be eligible for SBRT, or re-initiation of MK-3475.

Patients will be treated on non-consecutive days whenever possible, with all fractions to be scheduled within 15 calendar days from first to last. Localization of the tumor target before each fraction is required, by either cone-beam CT scan, kilovoltage on -board imaging, or an internal fiducial.

SBRT Dose Modification and Supportive Care

SBRT will be discontinued if any grade 3 or greater adverse event occurs during radiation treatment that is probably or definitely attributable to radiation. This will be counted as a DLT if it occurs during the phase Ib portion of the study. These patients will be allowed to continue with trial therapy (the second course of MK-3475, but not the remainder of their SBRT) if the toxicity resolves to grade 0 or 1 with supportive measures within 12 weeks of AE start date.

SBRT will also be discontinued if the completion of all fractions is prolonged beyond 30 days for reasons unrelated to toxicity (i.e., intercurrent illness, or patient refusal). This will not be counted as a DLT, and these patients will be allowed to continue with trial therapy (the second course of MK-3475, but not the remainder of their SBRT) as long as the investigator believes that they will be compliant with the remainder of the trial therapy. In the phase Ib portion of the study, these patients will not be counted towards the minimum number of patient treated at that dose level as long as they have not experienced a DLT before treatment is abort, but instead will be replaced. If they have experienced a DLT during that period, then they will be counted toward that dose cohort.

No other SBRT dose modification for individual patients is permitted during the phase Ib portion of the study. During the phase 2a portion, at the discretion of the treating radiation oncologist and with the agreement of the principal investigator, the prescription dose for SBRT may be reduced in an effort to reduce the risk of toxicity. In this case, one of the 3 dose levels specified in the dose escalation section 5.3 will be used.

Adverse events that occur during or after SBRT should be managed per section 5.5, or with best supportive care.

53 SBRT Dose-Escalation or De-Escalation

In the Phase 1b (SBRT dose escalation/de-escalation) portion, patients will be allocated to Arm A (Lung) or Arm B (non-Lung) based on the anatomic site of the target chosen for SBRT. Dose escalation or de-escalation will be done separately for each arm, and the MTD determined separately for each arm. Once an MTD has been determined for lung and non-lung targets, future patients with those SBRT targets will be allocated to the Phase IIa portion of the trial.

In the Phase 2a (expansion) portion, patients will be treated at the SBRT MTD for lung or non-lung lesions, as appropriate.

Dose-Escalation or De-Escalation

In the Phase Ib portion of the trial, the SBRT dose will be escalated or de-escalated in successive cohorts. The starting dose will be 3000 cGy in 5 fractions. A single de-escalation cohort (1000 cGy in a single fraction), and a single escalation cohort (3000 cGy in 3 fractions) will be allowed.

Because SBRT target selection and treatment will occur in a rolling fashion after a patient progresses on the pre-SBRT MK-3475, availability for enrollment on the dose escalation cohorts will be somewhat unpredictable. In an effort to maximize the number of available treatment slots, enrollment in the dose escalation arms will be done using a “Rolling Six” design, following the guidelines in Table 5, below[56]. A minimum of two patients will be enrolled at each dose level. After 2 patients have been enrolled, the treatment cohort will be determined by the number of patients enrolled, the number who have experienced a DLT, the number who have not, and the number who have not yet completed the DLT follow-up period. The rolling enrollment design allows more than three patients to be enrolled within a dose cohort before safety has been demonstrated, and reflects the fact that both MK-3475 and SBRT have demonstrated safety at higher doses than prescribed in this protocol, as single agents.

If the lowest dose cohort of 1000 cGy in a single fraction is not completed with acceptable toxicity, those targets (i.e., lung or non-lung) will be excluded from the remainder of the study. If neither arm is able to be completed at the lowest SBRT dose level, the study will be terminated. If the highest dose level of 3000 cGy is reached and successfully completed, that will be the MTD for the phase IIA portion of the study. A minimum of 6 patients will be treated at the MTD in the phase Ib portion of the study.

Table 5.

Enrolled	DLT	No DLT	In follow-up	Cohort to enroll
2	0, 1	Any	Any	Enroll at same dose level
2	2	Any	Any	Enroll at lower dose level
3	0	0, 1, 2	3, 2, 1	Enroll at same dose level
3	0	3	0	Enroll at higher dose level*
3	1	0, 1, 2	2, 1, 0	Enroll at same dose level
3	≥ 2	Any	Any	Enroll at lower dose level
4	0	0, 1, 2, 3	4, 3, 2, 1	Enroll at same dose level
4	0	4	0	Enroll at higher dose level*
4	1	0, 1, 2, 3	3, 2, 1, 0	Enroll at same dose level

4	≥ 2	Any	Any	Enroll at lower dose level
5	0	0,1,2,3,4	5,4,3,2,1	Enroll at same dose level
5	0	5	0	Enroll at higher dose level*
5	1	0,1,2,3,4	4,3,2,1,0	Enroll at same dose level
5	≥ 2	Any	Any	Enroll at lower dose level
6	0	0,1,2,3,4	6,5,4,3,2	SUSPEND enrollment
6	0	5, 6	1, 0	Enroll at higher dose level**
6	1	0,1,2,3,4	5,4,3,2,1	Suspend enrollment
6	1	5	0	Enroll at higher dose level**
6	≥ 2	Any	Any	Enroll at lower dose level

*At the maximum dose level, continue current dose cohort

**At the maximum dose level, STOP, this is the MTD

Definition of Dose Limiting Toxicity

For the purpose of determining the MTD of SBRT, a DLT will be considered to be any of the following adverse events which are probably or definitely attributable to study treatment, and which occur between the first fraction of SBRT and within 60 days of the last fraction of SBRT.

1. Any non-hematologic, non-laboratory toxicity which is grade 3 or greater and does not resolve to grade 2 or lower with supportive care within 14 days.
2. Any non-hematologic, non-laboratory toxicity which is grade 4 or greater
3. For patients in Arm A (lung targets), the development of grade 3 or greater pneumonitis that is probably or definitely attributable to either SBRT or MK-3475 within the follow-up period will be considered a DLT, regardless of whether it resolves.

54 Concomitant Medications/Vaccinations (allowed & prohibited)

Acceptable Concomitant Medications

All treatments that the investigator considers necessary for a subject's welfare may be administered at the discretion of the investigator in keeping with the community standards of medical care. All concomitant medication will be recorded on the case report form (CRF) including all prescription, over-the-counter (OTC), herbal supplements, and IV medications and fluids. If changes occur during the trial period, documentation of drug dosage, frequency, route, and date may also be included on the CRF.

All concomitant medications received within 28 days before the first dose of trial treatment and 30 days after the last dose of trial treatment should be recorded. Concomitant medications administered after 30 days after the last dose of trial treatment should be recorded for SAEs as defined in Section 7.2.

Prohibited Concomitant Medications

Subjects are prohibited from receiving the following therapies during the Screening and Treatment Phase (including retreatment for post-complete response relapse) of this trial:

- Anti-cancer systemic chemotherapy or biological therapy
- Immunotherapy not specified in this protocol
- Chemotherapy not specified in this protocol
- Investigational agents other than MK-3475
- Radiation therapy except for that specified by protocol
- Live vaccines within 30 days prior to the first dose of trial treatment and while participating in the trial. Examples of live vaccines include, but are not limited to, the following: measles, mumps, rubella, chicken pox, yellow fever, rabies, BCG, and typhoid (oral) vaccine. Seasonal influenza vaccines for injection are generally killed virus vaccines and are allowed; however intranasal influenza vaccines (e.g. Flu-Mist®) are live attenuated vaccines, and are not allowed.
- Systemic glucocorticoids for any purpose other than to modulate symptoms from an event of clinical interest of suspected immunologic etiology. The use of physiologic doses of corticosteroids may be approved after consultation with the Sponsor.

Subjects who, in the assessment by the investigator, require the use of any of the aforementioned treatments for clinical management should be removed from the trial. Subjects may receive other medications that the investigator deems to be medically necessary.

There are no prohibited therapies during the Post-Treatment Survival Follow-up Phase.

55 Rescue Medications & Supportive Care

Supportive Care Guidelines

Subjects should receive appropriate supportive care measures as deemed necessary by the treating investigator. Suggested supportive care measures for the management of adverse events with potential immunologic etiology are outlined below. Where appropriate, these guidelines include the use of oral or intravenous treatment with corticosteroids as well as additional anti-inflammatory agents if symptoms do not improve with administration of corticosteroids. Note that several courses of steroid tapering may be necessary as symptoms may worsen when the steroid dose is decreased. For each disorder, attempts should be made to rule out other causes such as metastatic disease or bacterial or viral infection, which might

require additional supportive care. The treatment guidelines are intended to be applied when the investigator determines the events to be related to pembrolizumab.

Note: if after the evaluation the event is determined not to be related, the investigator does not need to follow the treatment guidance (as outlined below). Refer to Section 5.2.1 for dose modification.

It may be necessary to perform conditional procedures such as bronchoscopy, endoscopy, or skin photography as part of evaluation of the event.

- Pneumonitis:
 - For Grade 2 events, treat with systemic corticosteroids. When symptoms improve to Grade 1 or less, steroid taper should be started and continued over no less than 4 weeks.
 - For Grade 3-4 events, immediately treat with intravenous steroids. Administer additional anti-inflammatory measures, as needed.
 - Add prophylactic antibiotics for opportunistic infections in the case of prolonged steroid administration.
- Diarrhea/ Colitis: Subjects should be carefully monitored for signs and symptoms of enterocolitis (such as diarrhea, abdominal pain, blood or mucus in stool, with or without fever) and of bowel perforation (such as peritoneal signs and ileus).
 - When symptoms improve to Grade 1 or less, steroid taper should be started and continued over no less than 4 weeks.
 - For Grade 2 diarrhea/ colitis, administer oral corticosteroids.
 - For Grade 3 or 4 diarrhea/ colitis, treat with intravenous steroids followed by high dose oral steroids. All subjects who experience diarrhea/ colitis should be advised to drink liberal quantities of clear fluids. If sufficient oral fluid intake is not feasible, fluid and electrolytes should be substituted via IV infusion. For grade 2 or higher diarrhea, consider GI consultation and endoscopy to confirm or rule out colitis.
- Type 1 diabetes mellitus (if new onset, including diabetic ketoacidosis [DKA]) or \geq Grade 3 Hyperglycemia, if associated with ketosis (ketonuria) or metabolic acidosis (DKA)
 - For T1DM or Grade 3-4 Hyperglycemia

- Insulin replacement therapy is recommended for Type I diabetes mellitus and for Grade 3-4 hyperglycemia associated with metabolic acidosis or ketonuria.
- Evaluate patients with serum glucose and a metabolic panel, urine ketones, glycosylated hemoglobin, and C-peptide.
- Hypophysitis:
 - For Grade 2 events, treat with corticosteroids. When symptoms improve to Grade 1 or less, steroid taper should be started and continued over no less than 4 weeks. Replacement of appropriate hormones may be required as the steroid dose is tapered.
 - For Grade 3-4 events, treat with an initial dose of IV corticosteroids followed by oral corticosteroids. When symptoms improve to Grade 1 or less, steroid taper should be started and continued over no less than 4 weeks. Replacement of appropriate hormones may be required as the steroid dose is tapered.
- Hyperthyroidism or Hypothyroidism:

Thyroid disorders can occur at any time during treatment. Monitor patients for changes in thyroid function (at the start of treatment, periodically during treatment, and as indicated based on clinical evaluation) and for clinical signs and symptoms of thyroid disorders.

 - Grade 2 hyperthyroidism events (and Grade 2-4 hypothyroidism):
 - In hyperthyroidism, non-selective beta-blockers (e.g. propranolol) are suggested as initial therapy.
 - In hypothyroidism, thyroid hormone replacement therapy, with levothyroxine or liothyroinine, is indicated per standard of care.
 - Grade 3-4 hyperthyroidism
 - Treat with an initial dose of IV corticosteroid followed by oral corticosteroids. When symptoms improve to Grade 1 or less, steroid taper should be started and continued over no less than 4 weeks. Replacement of appropriate hormones may be required as the steroid dose is tapered.
- Hepatic:
 - For Grade 2 events, monitor liver function tests more frequently until returned to baseline values (consider weekly).
 - Treat with IV or oral corticosteroids

- For Grade 3-4 events, treat with intravenous corticosteroids for 24 to 48 hours.
- When symptoms improve to Grade 1 or less, a steroid taper should be started and continued over no less than 4 weeks.
- Renal Failure or Nephritis:
 - For Grade 2 events, treat with corticosteroids.
 - For Grade 3-4 events, treat with systemic corticosteroids.
 - When symptoms improve to Grade 1 or less, steroid taper should be started and continued over no less than 4 weeks.
-

Management of Infusion Reactions: Signs and symptoms usually develop during or shortly after drug infusion and generally resolve completely within 24 hours of completion of infusion. Table 6 below shows treatment guidelines for subjects who experience an infusion reaction associated with administration of MK-3475.

Table 6 Infusion Reaction Treatment Guidelines

NCI CTCAE Grade	Treatment	Premedication at subsequent dosing
Grade 1 Mild reaction; infusion interruption not indicated; intervention not indicated	Increase monitoring of vital signs as medically indicated until the subject is deemed medically stable in the opinion of the investigator.	None
